Appendix N. C-SSRS Scoring Rules

The following outcomes are C-SSRS categories and have binary responses (yes/no). The categories have been re-ordered from the actual scale to facilitate the definitions of the composite and comparative endpoints, and to enable clarity in the presentation of the results.

Category 1 – Wish to be Dead

Category 2 – Non-specific Active Suicidal Thoughts

Category 3 – Active Suicidal Ideation with Any Methods (Not Plan) without Intent to Act

Category 4 – Active Suicidal Ideation with Some Intent to Act, without Specific Plan

Category 5 – Active Suicidal Ideation with Specific Plan and Intent

Category 6 – Preparatory Acts or Behavior

Category 7 – Aborted Attempt

Category 8 – Interrupted Attempt

Category 9 – Actual Attempt (non-fatal)

Category 10 – Completed Suicide

Self-injurious behavior without suicidal intent is also a C-SSRS outcome (although not suicide-related) and has a binary response (yes/no).

The following outcome is a numerical score derived from the C-SSRS categories.

- Suicidal Ideation Score: The maximum suicidal ideation category (1 – 5 on the C-SSRS) present at the assessment. Assign a score of 0 if no ideation is present.

Composite endpoints based on the above categories are defined below.

- Suicidal ideation: A "yes" answer at any time during treatment to any one of the five suicidal ideation questions (Categories 1 – 5) on the C-SSRS.
- Suicidal behavior: A "yes" answer at any time during treatment to any one of the five suicidal behavior questions (Categories 6 – 10) on the C-SSRS.
- Suicidal behavior ideation or behavior: A "yes" answer at any time during treatment to any one of the ten suicidal ideation and behavior questions (Categories 1 – 10) on the C-SSRS.

Comparative endpoints of interest are defined below. "Treatment emergence" is used for outcomes that include events that first emerge or worsen. "Emergence" is used for outcomes that include events that first emerge.

- Treatment-emergent suicidal ideation compared to recent history: An increase in the maximum suicidal ideation score during treatment from the maximum suicidal ideation category during a specified pre-treatment period (C-SSRS scales taken during the specified pre-treatment period; excludes "lifetime" scores from the Baseline C-SSRS scale or Baseline/Screening C-SSRS scale).
- Treatment-emergent serious suicidal ideation compared to recent history: An increase in the maximum suicidal ideation score to 4 or 5 on the C-SSRS during treatment from not having serious suicidal ideation (scores of 0 – 3) during a specified pre-treatment period (C-SSRS scales taken during the specified pretreatment period; excludes "lifetime" scores from the Baseline C-SSRS scale or Baseline/Screening C-SSRS scale).
- Emergence of serious suicidal ideation compared to recent history: An increase in the maximum suicidal ideation score to 4 or 5 on the C-SSRS during treatment from no suicidal ideation (scores of 0) during a specified pre-treatment period (CSSRS scales taken during the specified pre-treatment period; excludes "lifetime" scores from the Baseline C-SSRS scale or Baseline/Screening C-SSRS scale).
- Emergence of suicidal behavior compared to all prior history: The occurrence of suicidal behavior (Categories 6 – 10) during treatment from not having

suicidal behavior (Categories 6 – 10) prior to treatment (includes "lifetime" and/or "screening" scores from the Baseline C-SSRS scale, Screening C-SSRS scale, or Baseline/Screening C-SSRS scale, and any "Since Last Visit" from the Since Last Visit C-SSRS scales taken prior to treatment)

- Improvement in suicidal ideation at a time point of interest compared to baseline: An improvement in this endpoint can be considered as a decrease in suicidal ideation score at the time point of interest (e.g., the last measurement during treatment) from the baseline measurement (e.g., the measurement taken just prior to treatment). This analysis should only be performed for studies in which a baseline C-SSRS can be defined (i.e., having improvement from the worse event over a lifetime is not clinically meaningful).

**Appendix O. Health Care Resource Utilization Questionnaire (HCRU)
Version 2.0 – SAMPLE**

(To be completed by Site Staff)

Non-Study Visits for Routine/General Health Care

Version 2.0

Complete Version 2.0 for Subject's who randomize under Amendment 2

Instructions to Site Staff: At each scheduled monthly visit (Month 1 through Month 6) in the Treatment Period, please ask if the subject saw a *Non-Study* Health Care Practitioner (HCP) since her last scheduled monthly visit for a *routine/general health care visit that is not associated with an adverse event.*

Only record routine/general health care visits with Non-Study HCPs below.

Record Non-Study HCP Visits associated with an adverse event on the Adverse Event form only. Do not record below.

1. Since the Subject's last scheduled monthly study visit, has she seen a non-study Health Care Practitioner (e.g., Physician, Nurse Practitioner, Physician Assistant, Dentist, Physical Therapist) for a *routine/general health care visit that is not associated with an adverse event?* No Yes

If Yes, please complete the questions below.

Record Non-Adverse Event Related Visits Below		
Any Visits Associated with Adverse Events should be Recorded on the Adverse Event eCRF only	4. What type(s) of Non-Study Health Care Practitioner was the Subject seen by? (Check all that apply)	5. How many times was the subject seen by each Non-Study Health Care Practitioner?
2. What type of facility was the subject seen at?  Office	 AUDIOLOGIST  ALLERGIST  CARDIOLOGIST  DENTIST  DERMATOLOGIST  ENDOCRINOLOGIST  ENT  FAMILY PHYSICIAN  GASTROENTEROLOGIST  GYNECOLOGIST  HEMATOLOGIST  HEPATOLOGIST  IMMUNOLOGIST  INFECTIOUS DISEASE SPECIALIST  INTERNAL MEDICINE SPECIALIST  INTERNIST  MEDICAL GENETICIST  NEPHROLOGIST  NEUROSURGEON  NURSE  NURSE PRACTITIONER  OCCUPATIONAL THERAPIST  OPHTHALMOLOGIST	

		 ORTHOPEDIC SURGEON  OPTOMETRIST  PHYSIATRIST  PHYSICAL THERAPIST  PLASTIC SURGEON  PODIATRIST  PSYCHOLOGIST  PULMONOLOGIST  RADIOLOGIST  REPRODUCTIVE ENDOCRINOLOGIST  RHEUMATOLOGIST  SURGEON  UROLOGIST  UNKNOWN  OTHER HEALTH CARE PRACTITIONER <small>(specify type):</small>
 Urgent Care		 AUDIOLOGIST  ALLERGIST  CARDIOLOGIST  DENTIST  DERMATOLOGIST  ENDOCRINOLOGIST  ENT  FAMILY PHYSICIAN  GASTROENTEROLOGIST  GYNECOLOGIST  HEMATOLOGIST  HEPATOLOGIST

	 ALLERGIST
	 CARDIOLOGIST
	 DENTIST
	 DERMATOLOGIST
	 ENDOCRINOLOGIST
	 ENT
	 FAMILY PHYSICIAN
	 GASTROENTEROLOGIST
	 GYNECOLOGIST
	 HEMATOLOGIST
	 HEPATOLOGIST
	 IMMUNOLOGIST
	 INFECTIOUS DISEASE SPECIALIST
	 INTERNAL MEDICINE SPECIALIST
	 INTERNIST
	 MEDICAL GENETICIST
	 NEPHROLOGIST
	 NEUROSURGEON
	 NURSE
	 NURSE PRACTITIONER
	 OCCUPATIONAL THERAPIST
	 OPHTHALMOLOGIST
	 ORTHOPEDIC SURGEON
	 OPTOMETRIST
	 PHYSIATRIST
	 PHYSICAL THERAPIST
	 PLASTIC SURGEON

	 PODIATRIST  PSYCHOLOGIST  PULMONOLOGIST  RADIOLOGIST  REPRODUCTIVE ENDOCRINOLOGIST  RHEUMATOLOGIST  SURGEON  UROLOGIST  UNKNOWN  OTHER HEALTH CARE PRACTITIONER (specify type):
6. Did the Subject have any diagnostic or therapeutic procedures performed since the last scheduled monthly study visit?  No  Yes (If Yes, complete questions 7 and 8 below)	
7. Diagnostic/Therapeutic Procedure (Check all that apply)	
Ultrasound Scan	
Physical Examination	
Vital Signs	
MRI	
CT Scan	
X-Ray	
Biopsy and Histologic Examination	
Pelvic Exam	
Urine Test	
Blood Test	
Other (specify): _____	
8. How many times was the procedure performed?	

**Appendix P. Health Care Resource Utilization Questionnaire (HCRU)
Version 1.0 – SAMPLE**

(To be completed by Site Staff)

Non-Study Visits for Routine/General Health Care

Complete Version 1.0 for Subjects who randomized under Amendment 1

Instructions to Site Staff: At each scheduled monthly visit in the Treatment Period, please ask if the subject saw a *Non-Study* Health Care Practitioner (HCP) since her last scheduled monthly visit for a **routine/general health care visit that is not associated with an adverse event.**

Only record routine/general health care visits with Non-Study HCPs below.

Record Non-Study HCP Visits associated with an adverse event on the Adverse Event form only. Do not record below.

1. Since the Subject's last scheduled monthly study visit, has she seen a *non-study* Health Care Practitioner (e.g., Physician, Nurse Practitioner, Physician Assistant, Dentist, Physical Therapist) for a **routine/general health care visit?**

No Yes

If **Yes**, please complete questions 2 and 3 below to indicate the type(s) of *Non-Study Physician(s)* seen and the number of times each Non-Study Physician was seen.

2. What type(s) of Non-Study Physician Specialty was the Subject seen by? (Check all that apply)		3. How many times was the subject seen by each Non-Study HCP
AUDIOLOGIST		 1  2  3  4  5
ALLERGIST		 1  2  3  4  5
CARDIOLOGIST		 1  2  3  4  5
DENTIST		 1  2  3  4  5
DERMATOLOGIST		 1  2  3  4  5
ENDOCRINOLOGIST		 1  2  3  4  5
ENT		 1  2  3  4  5
FAMILY PRACTITIONER		 1  2  3  4  5
GASTROENTEROLOGIST		 1  2  3  4  5
GYNECOLOGIST		 1  2  3  4  5
HEMATOLOGIST		 1  2  3  4  5
HEPATOLOGIST		 1  2  3  4  5
IMMUNOLOGIST		 1  2  3  4  5
INFECTIOUS DISEASE SPECIALIST		 1  2  3  4  5
INTERNAL MEDICINE SPECIALIST		 1  2  3  4  5
INTERNIST		 1  2  3  4  5
MEDICAL GENETICIST		 1  2  3  4  5
NEPHROLOGIST		 1  2  3  4  5
NEUROSURGEON		 1  2  3  4  5
OPHTHAMOLOGIST		 1  2  3  4  5
ORTHOPEDIC SURGEON		 1  2  3  4  5
PHYSIATRIST		 1  2  3  4  5
PLASTIC SURGEON		 1  2  3  4  5
PODIATRIST		 1  2  3  4  5
PSYCHIATRIST		 1  2  3  4  5
PSYCHOLOGIST		 1  2  3  4  5
PULMONOLOGIST		 1  2  3  4  5
RHEUMATOLOGIST		 1  2  3  4  5
SURGEON		 1  2  3  4  5
UROLOGIST		 1  2  3  4  5
OTHER PHYSICIAN (specify type: _____)		 1  2  3  4  5

Appendix Q. Adverse Events of Special Interest

Item of Safety Interest	Method of Surveillance
Hot flashes	Non-bone related hypoestrogenic effects CMQ
Bone mineral density loss	Osteoporosis/Osteopenia SMQ DXA results from clinical trials
Anemia	Cases are identified through the Non-Hemolytic and Non-Aplastic Anemias CMQ Haematopoietic erythropenia SMQ
Bone Fractures	Osteoporosis/Osteopenia SMQ
Rash and hypersensitivity reactions	Anaphylactic reaction SMQ Severe cutaneous adverse reactions SMQ Drug induced rash CMQ
Lipid abnormalities	Dyslipidemia SMQ
Uterine bleeding change	Female reproductive bleeds CMQ
Endometrial safety	Uterine and fallopian tube neoplasms, malignant and unspecified SMQ Reproductive Premalignant Disorders SMQ Endometrial biopsy results
Hypoestrogenic AEs (excluding hot flashes, BMD loss, and fractures)	Non-bone related hypoestrogenic effects CMQ
Spontaneous abortion	Termination of pregnancy and risk of abortion SMQ
Teratogenicity	Review of pregnancy outcomes All pregnancies will be followed up to 6 to 12 months post-delivery and reviewed at least quarterly and as they occur
Obstetrical complications (maternal and infant)	Pregnancy, labor, and delivery complications and risk factors (excluding abortions and stillbirths) SMQ
Psychiatric events	Depression and suicide/self-injury SMQ
Cardiovascular events	Cardiac arrhythmias SMQ, Cardiomyopathy SMQ, and Ischemic heart disease SMQ
Thromboembolic events	Embolitic and thrombotic events SMQ

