6.1.1 Definitions

6.1.1.1 Adverse Event

An adverse event (AE) is defined as any untoward medical occurrence in a patient or clinical investigation subject administered a pharmaceutical product and which does not necessarily have a causal relationship with this treatment. An adverse event can therefore be any unfavorable and unintended sign (including an abnormal laboratory finding), symptom, or disease temporally associated with the use of a medicinal (investigational) product, whether or not the event is considered causally related to the use of the product.

Such an event can result from use of the drug as stipulated in the protocol or labeling, as well as from accidental or intentional overdose, drug abuse, or drug withdrawal. Any worsening of a pre-existing condition or illness is considered an adverse event. Worsening in severity of a reported adverse event should be reported as a new adverse event. Laboratory abnormalities, and vital signs are considered to be adverse events only if they result in discontinuation from the study, necessitate therapeutic medical intervention and/or if the investigator considers them to be adverse events.

An adverse event of amenorrhea will be reported for subjects who do not return to menses by the Post-Treatment Follow-up Month 2 Phone Visit and the adverse event will be followed until resolution. The onset date of the adverse event will be the date of the Follow-up Month 2 Visit.

A BMD decrease at any anatomic location (spine, total hip or femoral neck) during the Treatment or Post-Treatment Follow-up period that leads to discontinuation from study or a BMD decrease at any anatomic location with a T-score < -1.5 should be reported as an adverse event.

An elective surgery/procedure scheduled to occur during a study will not be considered an adverse event if the surgery/procedure is being performed for a pre-existing condition and the surgery/procedure has been pre planned prior to study entry. However, if the pre-existing condition deteriorates unexpectedly during the study (e.g., surgery performed earlier than planned), then the deterioration of the condition for which the elective surgery/procedure is being done will be considered an adverse event.

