6.1.1.3 Adverse Events of Special Interest

Some adverse events, such as adverse events of special interest (AESI), such as rash/hypersensitivity, fracture, neuro-psychiatric (depression, mood swings, etc.), vasomotor symptoms (hot flush, night sweats) or serious adverse events. AbbVie may require additional information, including family history, to be collected and recorded in the eCRF.

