8.1.8.2 Adverse Events

Adverse events (AEs) will be coded using the Medical Dictionary for Regulatory Activities (MedDRA) dictionary. Treatment-emergent adverse events (TEAEs) will be summarized for each treatment group. TEAEs are defined as AEs with a start date on or after the first dose of the study drug and within 30 days of the last dose of the study drug. AEs starting more than 30 days following discontinuation of the study drug will not be included in the summaries of TEAEs. AEs starting more than 30 days following discontinuation of the study drug will be summarized separately as Post-Treatment AEs.

When summarizing TEAEs by relationship or severity, if a subject has an event with unknown severity or relationship, then the subject will be counted in the severity/relationship category of "unknown," even if the subject has a second occurrence of the same event with a severity/relationship present. The only exception is if the subject has a second occurrence of the same event with the most extreme severity (i.e., "severe") or a relationship category of "reasonable possibility." In this case, the subject will be counted under these most extreme severity/relationship categories.

Frequencies and percentages of subjects with TEAEs will be calculated for each treatment group as follows:

- Any event
- By system organ class, and preferred term
- By system organ class, preferred term and maximum relationship
- By system organ class, preferred term and maximum severity

- Any event and by system organ class and preferred term for events resulting in study drug discontinuation
- Any event and by system organ class and preferred term for serious events
- Any event and preferred term for AESI's (e.g., hypoestrogenic adverse events)

The Post-Treatment AEs will be summarized in a similar manner as the TEAEs described above.

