12.2 Adverse Events

Adverse events (AEs) will be summarized using system organ classes (SOCs) and preferred terms (PTs) from the Medical Dictionary for Regulatory Activities (MedDRA) Version 19.0 or higher.

For each AE summary, the number and percentage of subjects experiencing at least one AE will be presented. Subjects reporting more than one AE within a SOC will be counted only once for that SOC. Subjects reporting more than one AE for a PT will be counted only once for that PT.

Treatment-emergent AEs are defined as AEs with a start date on or after the first dose of study drug. AEs starting more than 30 days following discontinuation of study drug will not be included in summaries of treatment-emergent AEs. Post-Treatment AEs are defined as AEs starting more than 30 days following discontinuation of study drug in the Treatment Period of this study.

When summarizing AEs by relationship or severity, if a subject has an event with unknown severity or relationship then the subject will be counted in the severity/relationship category of "unknown" even if the subject has a second occurrence of the same event with a severity/relationship present. The only exception is if the subject has a second occurrence of the same event with the most extreme severity (i.e., "severe") or one of the two most extreme relationship categories (i.e., "probably related" or "possibly related"). In this case, the subject will be counted under these most extreme severity/relationship categories.

Treatment Period

The number and percentage of subjects with treatment-emergent AEs will be calculated by treatment group as follows:

- Any AEs
- Any AEs by system organ class (SOC) and preferred term (PT)
- Any AEs occurring in $\geq 5\%$ of subjects by system organ class (SOC) and preferred term (PT)
- Any AEs by PT in descending frequency of elagolix 300 mg BID plus E2/NETA treatment group
- Any AEs by maximum severity
- Any AEs by maximum relationship
- Any AEs reasonably possibly related to study drug
- Any AEs leading to study drug discontinuation
- Any serious AEs (SAEs)
- Any SAEs reasonably possibly related to study drug

- Any SAEs leading to study drug discontinuation
- Any AEs of special interest as specified in [Appendix Q](#)
- Any AEs leading to death

A listing by treatment group of treatment-emergent AEs with subject IDs will be generated. Listings of all treatment-emergent SAEs, AEs leading to death, and AEs leading to study drug discontinuation will be generated.

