Summary of total number of hot flush and night sweat by subject-reported severity categories, summary of total number of hot flush and night sweat by maximum subject-reported severity, and summary of time to first onset of hot flush and night sweat will be provided. Listings of subjects associated with hot flush and night sweat will also be provided.

Post-Treatment Follow-Up Period

The Post-Treatment AEs will be summarized as follows:

- Any AEs
- Any SAEs.

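### SAP Appendix Q gives bone fractures and bone-density loss the same adverse-event query, and SAP 12.2 leaves out the post-treatment special-interest summary that Protocol 8.1.8.2 implies

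*SAP*

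**What the plan says.** **Definition of the items.** SAP Appendix Q pairs each item of safety interest with a way of finding it. For bone-density loss the entry is "Osteoporosis/Osteopenia SMQ DXA results from clinical trials". The fracture row reads "Bone Fractures Osteoporosis/Osteopenia SMQ". A further row begins "Hypoestrogenic AEs (excluding hot flashes, BMD loss, and fractures", so the appendix itself treats density loss and fractures as separate items.

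**Use of the items.** The treatment-period list in SAP 12.2 includes "Any AEs of special interest as specified in", followed by a reference to Appendix Q.

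**Protocol background.** Protocol 6.1.1.3 names fracture among its examples of special-interest events: "rash/hypersensitivity, fracture, neuro-psychiatric". Protocol 6.1.1.1 makes some density findings adverse events in their own right. One trigger is a decrease that leads to discontinuation from the study. The other is stated as "a BMD decrease at any anatomic location with a T-score < -1.5 should be reported as an adverse event".

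**After treatment.** Protocol 8.1.8.2 lists the summaries for treatment-emergent events, among them special-interest events overall and by preferred term. It then states: "The Post-Treatment AEs will be summarized in a similar manner as the TEAEs". The SAP 12.2 paragraph on follow-up opens "The Post-Treatment AEs will be summarized as follows" and has two entries: all adverse events and all serious adverse events.

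**The concern.** The study's second objective is to describe what E2/NETA does to the safety of elagolix, with bone density named explicitly. Fracture is a clinical outcome. A density decrease reported as an adverse event is a scan finding. A special-interest summary that cannot tell them apart does not answer the question for which fracture was singled out.

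The follow-up gap adds to this. Women whose density fell by 8% or more at Month 6 cannot enter the extension study and go into this follow-up instead (Protocol 5.3.1.1). Adverse events are collected there to Month 6 or Month 12 (Protocol 6.1.4). For most of that time the SAP plans no special-interest output, and it gives no reason for being narrower than the protocol.

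**Working it through.** The plan states no figure on this point, so there is nothing to reproduce. The check compares the texts and then sizes the uncovered part of follow-up.

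**Step 1. The two bone items.**

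| Appendix Q item | Adverse-event query | Other source |
|---|---|---|
| Bone-density loss | Osteoporosis/Osteopenia SMQ | DXA results |
| Bone fractures | Osteoporosis/Osteopenia SMQ | none |

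Let S be the set of women with at least one treatment-emergent event caught by the SMQ. The adverse-event count is |S| for density loss and |S| for fractures, so the difference is 0 whatever terms the SMQ holds. There are three cases:

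- If the SMQ holds only density terms, the fracture item contains no fractures.
- If it holds only fracture terms, the adverse-event part of the density item contains no density decreases.
- If it holds both, each item mixes the two.

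In no case does one item count fractures while the other counts density-loss events. If SAP 12.2 is read as asking for a single pooled special-interest row, there is no separate fracture count either.

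**Step 2. Post-treatment summaries.**

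| | Protocol 8.1.8.2 | SAP 12.2 |
|---|---|---|
| All events | yes | yes |
| Serious events | yes | yes |
| Special-interest events by preferred term | yes, carried over from the treatment-emergent list | not listed |

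The treatment-period list in SAP 12.2 has all events as one entry and all events by organ class and preferred term as another. Only the first recurs after treatment. The listing of events with subject identifiers is also confined to treatment-emergent events.

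**Step 3. Time without a special-interest summary.** The inputs are a 28-day month (Protocol 1.3) and a treatment-emergent window that closes 30 days after the last dose (Protocol 8.1.8.2 and SAP 12.2).

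- 12-month follow-up: 12 × 28 = 336 days; 336 − 30 = 306; 306/336 = 91%.
- Women who stopped before Month 3 and finish at follow-up Month 6: 6 × 28 = 168 days; 168 − 30 = 138; 138/168 = 82%.

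**Step 4. Where follow-up scans fall.** Follow-up DXA is nominally at days 168 and 336 after the last dose (SAP Table 8) and may be up to 15 days early (Protocol Table 1). The earliest in-window days are 168 − 15 = 153 and 336 − 15 = 321. Both lie well beyond day 30. A density event dated from either scan would therefore be a post-treatment event.

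**The case against.** The strongest reply is that little information is lost. For the Treatment Period, SAP 12.2 plans all events by organ class and preferred term, by preferred term in descending frequency, and in a listing with subject identifiers. Fracture terms and density terms appear there on separate lines. A reader might infer that fractures cannot be separated from density findings anywhere in the report; these tables rule that out for the Treatment Period.

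Density itself does not depend on the special-interest rows. SAP 12.4.1 compares DXA change between arms, including elagolix alone against elagolix plus E2/NETA, and SAP 12.4.2 summarises follow-up scans. Those results are untouched, although neither section counts fractures.

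Appendix Q can also be read as a surveillance table, since its second column includes entries that are not event queries, such as review of pregnancy outcomes. Protocol 3.2.2 mentions density decrease and fractures together. But SAP 12.2 points to this appendix for its summary, no other definition is given, and the appendix chose two rows.

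On follow-up, later fractures still fall under all events or all serious events, and SAP 12.2 opens with a general statement that events are summarised by organ class and preferred term. If that applies after treatment, fracture terms would appear. The separate entries noted in Step 2 suggest otherwise, so the SAP is ambiguous. A reader might conclude that follow-up fractures will not be tabulated at all; the documents do not establish that. The missing special-interest summary stands on either reading.

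Hot flashes share a query with the wider hypoestrogenic item in the same way. This is minor: SAP 12.2 plans separate analyses of hot flush and night sweat by severity and time to onset, with listings.

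**Conclusion.** Two defects stand. The Appendix Q rule cannot produce a fracture item distinct from the adverse-event part of the density-loss item. SAP 12.2 also conflicts with Protocol 8.1.8.2 on post-treatment special-interest events, leaving 91% of a full 12-month follow-up and 82% of a 6-month follow-up without that summary. These shares apply only to women who enter and complete follow-up here; those moving to the extension study have none in this trial. The conclusion needs no assumption about what the SMQ contains.

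Two stronger readings are tempting and unsupported:

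- **Direction of bias.** A reader might infer that scan-driven events would inflate fractures on elagolix alone and flatter E2/NETA. The content of the SMQ is not in the documents, so neither the bias nor its direction can be shown.
- **A count of false fractures.** A reader might apply the Phase 2b share with at least 8% spinal loss on elagolix alone (8%, Protocol 3.2.2) to 100 women. That loss is not what makes a density decrease an adverse event under Protocol 6.1.1.1; the triggers are study discontinuation or the T-score threshold. No document links the two rates.

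The point concerns the clarity and completeness of safety reporting. It changes no efficacy or DXA inference, and SAP 12.1 plans no safety testing after treatment.

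**What to change.** 1. In Appendix Q, give bone fractures a fracture-specific query or preferred-term list, distinct from the one used for bone-density loss.
2. In the follow-up part of SAP 12.2, add special-interest events by item and preferred term, as Protocol 8.1.8.2 provides. If the sponsor prefers the shorter list, the SAP should say that it departs from the protocol and why.
3. State in the same place whether the post-treatment summary of all events is broken down by organ class and preferred term.
4. Optionally, name the terms that define the hot-flash item.

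The cost is SAP wording, short term lists and one further table from adverse events already collected and coded. No new data, visits or change to the sample size are needed.
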